8.2.1.3 Toxicology

The toxicity profile of E-WE thrombin was evaluated in two GLP single-dose acute toxicity studies in Sprague-Dawley rats and cynomolgus monkeys. In rats, a single dose of E-WE thrombin was administered at doses of 0, 30, 100, and 300 µg/kg and animals were evaluated for 3 days (main study) and 29 days (recovery group) after dosing. In cynomolgus monkeys, a single dose of E-WE thrombin was administered at doses of 0, 12.5, 25, and 50 µg/kg and animals were evaluated for 4 days (main study) and 15 days (recovery study) after dosing. E-WE thrombin was well tolerated in both species and no E-WE thrombin-related AEs, apart from the temporal aPTT prolongation outside the reference range (the anticipated systemic effect at high doses), were observed. Based on these results, the no observed adverse effect level (NOAEL) was determined to be 300 µg/kg/dose and 50 µg/kg/dose, for rats and cynomolgus monkeys, respectively.

8.2.2 Clinical Studies

A first-in-human (FIH) study (Study No. EWE-17-01 [Celerion Project No.: CA19169]) was completed in the US on 25 November 2018. This study was a single ascending dose study in

healthy adult male and female subjects with the purpose of collecting safety, tolerability, and PD information in order to support further development of E-WE thrombin. A total of 21 male and female subjects were evaluated following IV bolus injection of one of four doses of E-WE thrombin (0.5, 1, 2, 4 µg/kg).

All 21 subjects who entered the study received the study medication or placebo and completed the study per protocol. Below is a summary of the preliminary data from this FIH study as of 24 of January 2019.

8.2.2.1 Safety Data

There were no deaths or serious AEs (SAEs) experienced in Study No. EWE-17-01 [Celerion Project No.: CA19169]. No subjects were discontinued due to AEs.

Overall, 4 of 21 (19%) subjects experienced a total of 8 treatment-emergent AEs (TEAEs) in this study, with 3 of 16 (19%) subjects following active treatment and 1 of 5 subjects (20%) following placebo. The majority of the events (5) were mild (Grade 1) in severity and 3 were moderate (Grade 2). Of the 8 TEAEs reported, only one was suspected to be possibly treatment related by the Principal Investigator (PI).

The most common TEAE was headache, experienced by 2 (13%) active-treatment subjects. One case of headache of moderate severity (Grade 2) was deemed to be possibly treatment related by the PI and had a reported onset of approximately 10 minutes after dosing, resolving 36 hours later. The other case of headache (Grade 1) was deemed to be unrelated to treatment by the PI and was reported 17 days after dosing, resolving 24 hours later. Other TEAEs reported included back pain, pruritus, papular rash and skin exfoliation in one placebo subject and vessel puncture site hemorrhage at the site of IV attempt in one active treatment subject.

Temporal aPTT prolongation was not evaluated as an AE, because it was an expected response, indicating a natural response to activation of endogenous protein C and release of some APC into systemic circulation.

A single IV dose of E-WE thrombin up to 4 µg/kg appeared to be safe and generally well tolerated by the healthy male and female subjects in this study.

[figure not shown]
8.2.2.2 Pharmacodynamic Data

The APC-PCI was used as a surrogate biomarker for drug exposure.

Mean plasma APC-PCI concentration results following single IV doses of E-WE thrombin are presented in [Figure 1](#). Plasma APC-PCI was detectable in all subjects at the first sampling time point of 0.08 hour (5 minutes) post-injection and remained detectable throughout the entire sampling interval in all subjects up to 2 hours in the 0.5 µg/kg dose level group and up to 4 hours in the 1, 2 and 4 µg/kg dose level groups. Plasma concentrations of APC-PCI increased in a temporal and dose-dependent manner. All concentrations returned to baseline by 24 hours. Peak mean APC-PCI concentrations occurred at 0.5 hour (30 minutes) in all dose level groups. Ascending doses of E-WE thrombin increased the peak and overall

[figure not shown]
APC-PCI concentrations in a dose-proportional manner from the 0.5 to 2 $\mu\text{g}/\text{kg}$ dose levels, and slightly less than dose-proportional from the 2 to 4 $\mu\text{g}/\text{kg}$.

Figure 1. APC-PCI Complexes after E-WE Thrombin Administration in Healthy Subjects

Anticoagulation was verified by a temporal, dose-dependent increase in the aPTT, which returned to baseline by 4 hours (in the 0.5 and 1 $\mu\text{g}/\text{kg}$ groups) and by 24 hours (in the 2 and 4 $\mu\text{g}/\text{kg}$ groups). Administration of E-WE thrombin did not significantly impact prothrombin time (PT), platelets or fibrinogen levels (Figure 2). In the figure, laboratory reference ranges are shown with black dashed lines and clinically significant ranges are shown with red dashed lines.

Figure 2. Coagulation Parameters after E-WE Thrombin Administration in Healthy Subjects

8.3 Rationale

8.3.1 Purpose of the Study Design

A FIH study was conducted in healthy subjects and concluded that a single dose of E-WE thrombin up to 4 µg/kg, administered as a bolus, was safe and generally well tolerated. This study will explore antithrombotic potential and utility of single doses of E-WE thrombin administered as a bolus followed by an infusion in the treatment and prevention of thrombus formation in an extracorporeal device such as an HD cartridge.

Thromboembolic disease and bleeding are common comorbidities in patients with chronic kidney diseases [5]. In most ESRD patients, heparin is routinely used during outpatient HD to reduce clotting in the dialyzer cartridge and to improve HD efficiency. However, administration of heparin during HD temporally increases the risk of bleeding. A safe alternative for patients with active bleeding, patients with previously documented or acquired heparin-induced thrombocytopenia, or that are at high risk for bleeding complications, is heparin-free dialysis [6-8] and the majority of HD patients that are admitted to the hospital are routinely dialyzed without heparin due to bleeding concerns.

In this study design, patients will be confined to the clinic for the majority of the trial and will not receive heparin during their HD sessions. While heparin-free HD can increase clotting within the dialyzer, resulting in the need for exchange of the dialyzer cartridge during HD in 5-7% of the procedures [9], there is no evidence that HD without heparin results in increased thromboembolic complications. Indeed, heparin anticoagulation during HD is not intended for systemic thromboprophylaxis and a recent retrospective analysis of data from the United States Renal Data System and electronic medical records shows that heparin-free HD is not associated with increased risk of thromboembolic events in ESRD patients [10]. Therefore, the removal of standard of care heparin anticoagulation in either arm for the short duration of the study is not expected to be a clinically relevant safety risk, nor place the patients at an increased risk for development of thromboembolic complications. Additionally, it enables the most rigorous assessment of safety and efficacy for E-WE thrombin that would not be possible if heparin anticoagulation during HD was maintained.

E-WE thrombin is expected to reduce thrombogenesis by downregulating thrombin generation in the extracorporeal circuit and hemodialyzer without clinically significant impairment of the patient's hemostasis or promoting thrombosis. Both thromboembolism and bleeding are common comorbidities in ESRD patients on HD, and heparin for HD is not well tolerated in some patients, as about 4% of ESRD patients develop heparin-induced thrombocytopenia (HIT). Severe HIT is a life-threatening acute complication of heparin exposure. HIT antibodies have been detected in about 8% of HD patients who receive unfractionated heparin, and some of them are at risk of developing a severe HIT event. Thus, an intrinsically safe short-term and self-limiting anticoagulant as an alternative to heparin is currently an unmet need for this patient population. As such, E-WE thrombin administration during HD may be an effective method to protect the hemodialyzer from clot development, and stands as a promising, short-acting alternative to other anticoagulants in this population. It is therefore of interest to assess E-WE thrombin safety and effectiveness in ESRD patients on chronic HD.

A placebo arm is included in this study design in order to robustly demonstrate the safety and efficacy of E-WE thrombin while not placing the patients at unnecessary risk, as mentioned above. The primary endpoint in this study is safety, measured as the number or frequency/rate of AEs that occur during the comparable observation periods. A heparin-free inpatient HD observation period (from Day -8 to Day 1 prior to dosing) is included in the trial design to establish a baseline for the heparin-free procedure. Continuation of the heparin-free HD procedure during the subsequent trial period and inclusion of a placebo arm allows for the determination of whether an AE is drug-related or not and permits accurate assessment of the safety of the study drug. The addition of a placebo arm also removes potential bias from the interpretation of AEs by the PIs and from the reporting by the patients. The secondary endpoint for this study is efficacy of E-WE thrombin on HD which may be more clearly observed with a placebo control instead of an active control (e.g., heparin). While the placebo arm may be at the same risk of clotting within the dialysis circuit as during the pre-dosing period (Days -8 to 1), data cited above suggests that these patients will not be at higher risk for either thromboembolic or bleeding complications. Should clotting occur within the dialyzer cartridge during a HD session that results in dialyzer failure, the dialyzer cartridge will be replaced, and the patient will be closely monitored by

the PI. It is important to note that replacement of the dialyzer cartridge during HD is safe for the patient and a routine procedure in cases of dialyzer failure.

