- a For details on Procedures, refer to [Section 13](#).
- b Within 28 days prior to Day -8.
- c All patients who receive the study drug or matching placebo (including patients who terminate the study early) will return to the CRU on Day 14 (± 2 days) for coagulation tests, immunogenicity sample collection, and to determine if any AE has occurred since the last study visit.
- d Patients will be admitted to the CRU on Day -8, at the time indicated by the CRU, and will remain confined up to Day 3 or early termination.
- e During confinement to the CRU, patients will undergo HD 5 times: on Day -7, -5, -2, Day 1, and Day 3. For each patient, the HD will last approximately 4 hours as per patient standard schedule which will be the same throughout the study.
- f Symptom-driven physical examination may be performed at other times, at the PI's or designee's discretion.
- g To be performed within 1 hour prior to the start of HD.
- h To be performed at the end of HD.
- i The HD vascular access sites (AV fistula or AV graft puncture sites) are to be evaluated immediately after the end of HD and removal of the needles from the fistula or graft for bleeding cessation or other reactions.
- j Samples for serum chemistry will be obtained following a fast of at least 4 hours, however, in case of dropouts or rechecks, patients may not have fasted for 4 hours prior to the serum chemistry sample is taken.
- k For anuric patients, UA may not be performed.
- l Coagulation parameters include aPTT, PT/INR, fibrinogen, and TT.
- m A single dose of E-WE thrombin or matching placebo will be administered into the dialysis line according to the randomization schedule, upon initiation of the HD procedure. The dose will be administered as a bolus dose immediately followed by a continuous infusion over 4 hours. Hour 0 will correspond to the beginning of E-WE thrombin bolus administration.
- n The dialysate sample will be taken at 30 minutes and at 3 hours after the start of HD. The dialysate will be frozen and sent to Aronora.
- o To be performed when the dialyzer cartridge is removed and collected at the end of HD.
- p To be performed within approximately 20 minutes after completion of HD.

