9.2 Study Endpoints

Primary outcome measures:

- The safety and tolerability of E-WE thrombin following active treatment will be evaluated versus pre-treatment and placebo by number and severity of AEs (including HD vascular access site reactions), physical examinations, bleeding time from the HD vascular access sites, vital sign measurements, 12-lead ECGs, clinical laboratory tests, and coagulation tests.

Secondary outcome measures:

- PD of E-WE thrombin will be measured by APC-PCI and plasma APC-PCI will act as a surrogate marker for E-WE thrombin drug exposure.
- Efficacy of antithrombotic activity will be evaluated by thrombus accumulation within the dialyzer cartridge (evaluated by visual inspection) after E-WE thrombin active treatment versus pre-treatment and placebo.
- Efficiency of HD will be assessed using BUN levels before and after dialysis to determine urea removed by 4 hours of dialysis (Kt/V and URR) after E-WE thrombin active treatment versus pre-treatment and placebo.

Other outcome measures:

- Development of antibodies to E-WE thrombin or WT thrombin after drug exposure.

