10. INVESTIGATIONAL PLAN

10.1 Overall Study Design and Plan

This is a phase 2, randomized, double-blind, placebo-controlled, single-dose study of E-WE thrombin designed to evaluate the safety and efficacy at 2 dose levels administered to patients with ESRD during HD conducted at one study center in the US.

Patients will be enrolled in Cohort 1 or Cohort 2; cohorts will be dosed sequentially. Dosing of Cohort 2 will commence following completion of all study events for all patients in Cohort 1. Within each cohort, patients will be randomized to receive active drug or matching placebo as summarized below:

Table 1. Cohort and Treatment Randomization

Cohort	Treatment	Active:Placebo	Cohort Size
1	0.5 µg/kg bolus dose administered into the dialysis line immediately followed by a 0.25 µg/kg/hour continuous infusion dose into the dialysis line over 4 hours of E-WE thrombin or matching placebo, for a total dose of 1.5 µg/kg	2:1	12:6
2	1 µg/kg bolus dose administered into the dialysis line immediately followed by a 0.5 µg/kg/hour continuous infusion dose into the dialysis line over 4 hours of E-WE thrombin or matching placebo, for a total dose of 3 µg/kg	2:1	12:6

This study includes a screening period of 28 days prior to checking in to the CRU on Day -8. From Day -8 (8 days prior to dosing on Day 1) through Day 3, all patients will undergo HD 5 times and will be assessed for all scheduled procedures and endpoints before and after each HD session as per the Study Events Flow Chart ([Section 6](#)), using only one type of dialyzer cartridge for each patient.

On Day 1, prior to dosing, patients will undergo baseline measurements followed by initiation of a regular HD procedure, consistently using only one type of dialyzer cartridge for each patient. A single dose of E-WE thrombin or matching placebo will be administered into the dialysis line during the HD procedure. Patients will continue to undergo HD procedures and scheduled assessments from Day 1 through Day 3.

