10.1.1 Confinement, Return Visits, and Follow-Up

Patients will be admitted to the CRU on Day -8, at the time indicated by the CRU, until after completion of study procedures on Day 3 as indicated in the Study Events Flow Chart ([Section 6](#)). At all times, a patient may be required to remain at the CRU for longer at the discretion of the PI or designee.

All patients who receive the study drug or matching placebo (including patients who terminate the study early) will return to the CRU on Day 14 (\pm 2 days) for coagulation tests, immunogenicity sample collection, and to determine if any AE has occurred since the last study visit.

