13.2.8.2 Monitoring

Patients will be monitored for AEs from check-in through completion of the study. Patients will be asked how they are feeling once per day during confinement and at each return/follow-up visit.

AEs (whether serious or non-serious) and clinically significant abnormal laboratory test value(s) will be evaluated by the PI or designee and treated and/or followed up until the symptoms or value(s) return to normal, or acceptable levels, as judged by the PI or designee.

Treatment of SAEs will be performed by a licensed medical provider, either at the CRU or at a nearby hospital emergency room. Where appropriate, medical test(s) and/or examination(s) will be performed to document resolution of event(s). The outcome may be classified as resolved, improved, unchanged, worse, fatal, or unknown (lost to follow up).

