7.3 Adverse Events

All adverse events (AEs) occurring during this clinical trial will be coded using the Medical Dictionary for Regulatory Activities (MedDRA®), Version 21.1.

All AEs captured in the database will be listed in by-subject data listings including verbatim term, coded term, treatment, severity, relationship to study medication, and action; however, only treatment-emergent AEs (TEAEs) will be summarized.

A TEAE is defined as an AE that is starting or worsening at the time of or after study drug administration. Each TEAE will be attributed to a treatment based on the onset date and time of the AE. If the onset time of an AE is missing and the onset date is the same as the treatment dosing date, then the AE will be considered treatment emergent. If the onset date of an AE is missing, then the AE will be considered treatment emergent.

TEAEs will be tabulated by System Organ Class (SOC) and Preferred Term. Summary tables will include number of subjects reporting the AE and as percent of number of subjects dosed by treatment and overall. The number of AEs will be tabulated in a similar manner. Tables which tabulate the number of TEAEs by severity and relationship to study treatment will also be included.

Serious adverse events (SAEs), if present, will also be listed. Applicable narratives will be included in the CSR.

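### The pre-treatment part of the primary AE evaluation cannot be delivered as planned: run-in AEs are only listed, and the run-in and post-dose periods differ in length and in how AEs are collected

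*Protocol*

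**What the plan says.** Protocol 9.2, repeated in SAP 2.2, names two comparators for the primary outcome: active treatment "will be evaluated versus pre-treatment and placebo by number and severity of AEs". Protocol 8.3.1 describes the AE measure as "measured as the number or frequency/rate of AEs that occur during the comparable observation periods" and identifies the baseline: "A heparin-free inpatient HD observation period (from Day -8 to Day 1 prior to dosing". Neither document says which stretches of time are to be compared.

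The schedule fixes what is available. On run-in length and sessions, Protocol 10.1 states: "From Day -8 (8 days prior to dosing on Day 1) through Day 3, all patients will undergo HD 5 times". The flow chart notes give the dates: "patients will undergo HD 5 times: on Day -7, -5, -2, Day 1, and Day 3". Patients stay in the CRU until the Day 3 procedures are done. Protocol 10.1.1 then requires that everyone dosed, "including patients who terminate the study early) will return to the CRU on Day 14", with 2 days allowed either side, and that AEs since the previous visit be determined there. On questioning, Protocol 13.2.8.2 says: "Patients will be asked how they are feeling once per day during confinement and at each return/follow-up visit".

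SAP 7.3 lists all AEs but summarizes only those starting or worsening at or after dosing. The denominator is subjects dosed. Of event counts it says: "The number of AEs will be tabulated in a similar manner". No time at risk and no division of the post-dose period is defined. The AE tables in SAP 9.2 (14.3.1.1 to 14.3.1.3) contain no run-in column. SAP 8 nevertheless describes its analyses as aligned with the protocol.

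**The concern.** The within-patient comparison is part of the rationale for a small trial. Protocol 13.2.8.3 links recording AEs before, during and after exposure to needing fewer patients, and the trial has 24 active and 12 placebo patients. If the plan is followed exactly, that comparison is never tabulated. A reader who wants it must set listed run-in AEs beside treatment-emergent counts.

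Those two counts cover different lengths of time, different settings and different intensities of questioning. Adding a plain run-in count to the tables would not cure this. The answer would then depend on which post-dose window somebody chose after seeing the data: the whole period to Day 14 can make AEs look more frequent after dosing, and the confined part alone can make them look rarer, with no drug effect in either case.

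**Working it through.** **Inputs**
- Run-in: Day -8 to Day 1 before dosing, no Day 0, 8 days, all confined (Protocol 8.3.1, 10.1).
- HD sessions: 3 before dosing (Days -7, -5, -2) and 2 in the CRU from dosing on (Days 1, 3) (flow chart notes).
- Post-dose period: Day 1 to Day 14 ± 2, so 13 elapsed days, range 11 to 15 (Protocol 10.1.1).
- Confined post-dose time: Day 1 to Day 3, about 2 elapsed days (3 calendar days).
- Time outside the CRU: 13 − 2 = 11 days, or 11/13 = 85% of the post-dose period (9/11 = 82% to 13/15 = 87%).
- AE rate: not given in the documents, so assumed below.

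**The plan's own figure.** The only stated total that depends on these lengths is participation of approximately 50 days (Protocol 10.1.2). 28 (screening) + 8 (run-in) + 14 (Day 1 to Day 14) = 50; taking the flow chart's Day -37 to Day -9 as 29 days gives 51. The day counts agree with the protocol.

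**Expected count ratio with no drug effect.** Let the AE rate be constant and let f be the fraction of post-discharge AEs captured at the follow-up visit, with full capture while confined. Then post/pre = (2 + 11f)/8.

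| Capture f | Post/pre ratio |
|---|---|
| 0 (confined time only) | 2/8 = 0.25 |
| 0.25 | 4.75/8 = 0.59 |
| 0.50 | 7.5/8 = 0.94 |
| 6/11 = 0.55 | 8/8 = 1.00 |
| 0.75 | 10.25/8 = 1.28 |
| 1 | 13/8 = 1.63 |

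At f = 1 the visit window gives 11/8 = 1.38 to 15/8 = 1.88. Counting confined time as 3 calendar days gives 3/8 = 0.38 instead of 0.25.

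**Would a rate be enough?** Dividing by patient-days gives [(2 + 11f)/13]/1. This is 1.0 at full capture but 8/13 = 0.62 at f = 6/11. A rate over the whole period corrects for length, not for unequal capture.

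**What this could look like in 24 active patients**, with full capture, assumed rates and independent Poisson counts:

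| AEs per patient-day (assumed) | Expected pre (24 × 8 × rate) | Expected post (24 × 13 × rate) | Probability post exceeds pre |
|---|---|---|---|
| 0.02 | 3.8 | 6.2 | 0.725 |
| 0.05 | 9.6 | 15.6 | 0.865 |
| 0.10 | 19.2 | 31.2 | 0.949 |
| 0.20 | 38.4 | 62.4 | 0.991 |

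**Active versus placebo.** Every arm has the same schedule and the same questioning. With the same f, the expected per-patient ratio is (2 + 11f)/(2 + 11f) = 1.0.

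**Are matched windows available?** HD starts are 2, 3, 2 and 2 days apart (Days -7 to -5, -5 to -2, -2 to 1, 1 to 3). Windows of 48 hours from each start therefore do not overlap, and those for Days -7, -5, -2 and 1 lie within confinement. They cover 3 × 2 = 6 of the 8 run-in days and 2 post-dose days. At an assumed 0.05 AEs per patient-day, 24 active patients would give 24 × 6 × 0.05 = 7.2 events against 24 × 2 × 0.05 = 2.4, the same rate per patient-day.

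**The case against.** The strongest reply is that the trial already has a sound AE comparison. Active and pooled placebo share one post-dose window and one collection method, and Protocol 8.3.1 relies on the placebo arm, together with continued heparin-free dialysis, to judge drug-relatedness. That stands. A reader might infer that the primary AE comparison as a whole is biased by window length; the documents do not support this, because the randomized contrast is unaffected.

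Second, no table of pre- against post-dose counts is planned, so nobody is instructed to compute 13/8. That also stands. The defect is that a named comparison has no planned analysis and that the raw material for it is mismatched, not that a biased table has been specified.

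Third, Protocol 8.3.1 is a rationale section, its wording allows a frequency or rate, and it does not say that the whole run-in is to be set against the whole post-dose period. This is fair as far as it goes: the periods are undefined rather than wrongly defined. But the SAP defines no rate, and a rate over the whole period would leave unequal capture in place.

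Fourth, a reader might call the post-dose period mostly unobserved. That is too strong. Protocol 13.2.8.2 monitors AEs through study completion and the follow-up visit asks about the interval. The period is mostly outside the CRU with recall at one visit.

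Finally, AEs are one component of the primary outcome; bleeding time, coagulation and platelets are summarized session by session; and onset times are listed, so period rates could be recovered later. This limits the harm. It does not replace choosing the windows before unblinding.

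**Conclusion.** The concern holds for the pre-treatment comparison only. Followed exactly, the plan cannot deliver the AE evaluation against pre-treatment that Protocol 9.2 and SAP 2.2 name. Run-in AEs are not summarized, and the two periods differ in length (8 against about 13 days), confinement (all against about 2 days) and questioning (daily against one recall visit for about 11 days).

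The size and direction of the resulting imbalance are not fixed. With no drug effect, the post/pre count ratio ranges from about 0.25 to 1.63 (1.88 for a visit on Day 16), and equals 1.0 at about 55% capture after discharge. These figures assume a constant AE rate and full capture in the CRU. A reader might infer that counts must rise after dosing; that follows only under high post-discharge capture, which the documents do not establish.

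This should be corrected before unblinding. It does not undermine the randomized safety contrast.

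**What to change.** In SAP 7.3:
- Add a summary of run-in AEs by treatment arm.
- Define the pre-treatment comparison on matched confined windows, for example from the start of each HD session to 48 hours later, ended early if the next session starts sooner. Compare Days -7, -5 and -2 with Day 1.
- Report patients with an AE per window and AEs per patient-day, for each active dose and for pooled placebo. The placebo change addresses time order, which a pre/post contrast in active patients alone cannot.
- Show the remaining confined time on Day 3 and the outpatient time to follow-up as two separate periods.
- Keep the existing treatment-emergent tables to Day 14 as the active-versus-placebo contrast.

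Align the wording of Protocol 8.3.1 with these windows and record the addition in SAP 8.

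The 48-hour length is a choice, not a figure from the documents. It suits the session spacing, and it is consistent with the presumed half-life of seconds to minutes (Protocol 8.3.3) and with APC-PCI back at baseline by 24 hours in healthy subjects given a bolus (Protocol 8.2.2.2).

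The cost is some SAP text, a short set of tables and one derived period variable from onset dates and times already collected (Protocol 13.2.8.3). The downside is that fewer events fall in the matched windows, and about 2 of the 8 run-in days lie outside any window: check-in to the Day -7 session, and about 24 hours before the Day -2 session.
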